1. PEES
2. PedsQL-EoE

Final Assessment: (Week 12; day 84 +/- 14 days)

6. Pathologist Questionnaire (*maximum eos/hpf)
7. EREFs: Eosinophilic Esophagitis Endoscopic Reference Score)
8. PedsQL-EoE
9. PEES
10. Three-day diet diary
11. Review concomitant medications
12. Diet Review & Adherence Assessment
13. AE reporting

8.1 ADVERSE EVENTS AND SERIOUS ADVERSE EVENTS

8.1.1 DEFINITION OF ADVERSE EVENTS (AE)

An **Adverse Event (AE)** is defined as any new untoward medical occurrence or worsening of a pre-existing medical condition in a patient or clinical investigation participant administered an investigational (medicinal) product and that does not necessarily have a causal relationship with the treatment. An AE can therefore be any unfavorable and unintended sign (including an abnormal laboratory finding, for example), symptom, or disease temporally associated with the use of investigational product, whether or not considered related to the investigational product. Adverse events can be spontaneously reported or elicited during open-ended questioning, examination, or evaluation of a participant. (In order to prevent reporting bias, participants should not be questioned regarding the specific occurrence of one or more AEs.)

8.1.2 DEFINITION OF SERIOUS ADVERSE EVENTS (SAE)

A **serious AE (SAE)** is any untoward medical occurrence that at any dose:

- results in death
- is life-threatening (defined as an event in which the participant was at risk of death at the time of the event; it does not refer to an event which hypothetically might have caused death if it were more severe)
- requires inpatient hospitalization or causes prolongation of existing hospitalization (see **NOTE** below)
- results in persistent or significant disability/incapacity
- is a congenital anomaly/birth defect
- is an important medical event (defined as a medical event(s) that may not be immediately life-threatening or result in death or hospitalization but, based upon appropriate medical and scientific judgment, may jeopardize the participant or may require intervention [eg, medical, surgical] to prevent one of the other serious outcomes listed in the definition above.)

8.1.3 ADVERSE EVENT REPORTING

All adverse events will be reported to the principle investigator as soon as study staff are aware of the event. AEs that are not determined to be serious, will be recorded and reported to the IRB at the time of Continuing Review.

8.1.4 SERIOUS ADVERSE EVENT REPORTING

All SAEs will be reported to the lead coordinator/principle investigator within one business day of the first awareness of the event. The lead coordinator will complete the SAE CRF.

If the event meets fatal or life threatening criteria, it will be reported to the IRB within 24 hours of the first awareness of the event.

The Investigator must complete, sign and date the SAE CRFs and verify the accuracy of the information recorded on the SAE CRF with the corresponding source documents.

8.1.5 DEFINITION OF UNANTICIPATED PROBLEMS (UP)

In the event of an unanticipated problem, the investigator must assess whether it is expected, whether it is related to the research, and whether it puts other participants at increased risk for harm.

8.1.6 UNANTICIPATED PROBLEM REPORTING

If the event is unexpected, related, and puts participants at increased risk, the lead coordinator will notify the IRB immediately via the submission of a Report of Unanticipated Problems.

9 STATISTICAL CONSIDERATIONS

9.1 STATISTICAL HYPOTHESES

Based on histologic primary outcome efficacy estimates DED without PPI therapy (50%) compared to FREE (estimated 70%) a sample size of 36 enrolled patients per group (72 total) with 88% power, we will be able to demonstrate a detectable difference between the three groups, we assume the standard deviation for both groups to be 30%. We hypothesize that changes in primary and secondary endpoints for FREE participants will be superior to DED.

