1 PROTOCOL SUMMARY

1.1 SYNOPSIS

Title:	Food Additive Removal Diet for Pediatric Eosinophilic Esophagitis (FREE)
Study Description:	Prospective, pragmatic standard of care clinical trial comparing dietary therapies of dairy elimination diet (DED) to dairy + food additive elimination diet (FREE) in children with eosinophilic esophagitis.
Objectives:	
Primary Objective: To compare histologic outcomes (eosinophils per high power field: eos/hpf) of dairy elimination diet (DED) to dairy + food additive elimination diet (FREE) in children with eosinophilic esophagitis.
 
Secondary Objective: To compare endoscopic outcomes (Eosinophilic Esophagitis Endoscopic Reference scores: EREFs) of dairy elimination diet (DED) to dairy + food additive elimination diet (FREE) in children with eosinophilic esophagitis
 
Tertiary Objectives: To compare symptomatic (Pediatric Eosinophilic Esophagitis Symptom Severity Module v2.0: PEES) and quality of life (Peds-QL EoE Module 1) outcomes of dairy elimination diet (DED) to dairy + food additive elimination diet (FREE) in children with eosinophilic esophagitis

Endpoints:	
Primary Endpoint: (1) Histologic change differences of maximum eos/hpf baseline vs 12 week endoscopy
 
Secondary Endpoint: (1) EREFs: Eosinophilic Esophagitis Endoscopic Reference Score baseline vs 12 weeks
 
Tertiary Endpoints: (1) Patient Reported Outcomes (Pediatric Eosinophilic Esophagitis Symptom Severity Module (PEES) baseline vs 12 weeks, (2) quality of life (PedsQL-EoE)¹ baseline vs 12 weeks

Study Population:	We will plan to enroll 72 patients. Based on histologic primary outcome efficacy estimates of DED (50%) compared to FREE (estimated 70%) and a sample size of 36 enrolled patients per group (72 total) with 88% power, we will be able to demonstrate a detectable difference of 30% among two

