	
group comparisons. We estimate a 20% drop out rate among the diet elimination groups and analysis based on intention to treat.
 
Patients ≥ 2 - 18 years of age with isolated esophageal eosinophilia (≥ 15 eos/hpf). Patients with peripheral eosinophilia $> 1,500 \mu\text{L}$, concomitant GI inflammatory conditions, history of upper GI tract surgery (e.g. fundoplication), acid reflux by pH probe, severe developmental delay, have other medical conditions likely interfere with the study, has a significant psychiatric condition, has taken swallowed steroids in the last 8 weeks, or are not fluent in spoken and written English will be excluded.

Description of Sites/Facilities Enrolling Participants:
	
Participants will be enrolled nationally.

Description of Study Intervention:
	
Once patients meet eligibility criteria, they will be randomized to DED or FREE study groups. Participants will receive dietary education. Lead dietitians from each site will be identified and the approaches to dietary education will be standardized. Dietary education will be completed at the baseline visit and during follow up phone calls throughout the study.

Study Duration:
	
We anticipate this study will take 30 months to complete.
 
[December 31, 2017-----July 31, 2020]
 
Pre-trial Activities [-----] 7 mos
 
Enrollment/Intervention [-----] 16 mos
 
Data Collection [-----] 19 mos
 
Data Analysis [-----] 4 mos

Participant Duration:
	
Each participant will complete all study visits in 12 weeks +/-14 days.

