3 OBJECTIVES AND ENDPOINTS

OBJECTIVES	ENDPOINTS	JUSTIFICATION FOR ENDPOINTS
Primary		
To compare histologic outcomes of DED and FREE among children with eosinophilic esophagitis	Maximum eos/hpf (primary)	Eosinophils are a biomarker of inflammation. Current diagnostic criteria specify ≥ 15 eos/hpf. A reduction in eos/hpf should correlate with a reduction in symptoms. A successful treatment outcome is < 15 eos/hpf.
Secondary		
To compare endoscopic outcomes of DED and FREE among children with eosinophilic esophagitis	Eosinophilic Esophagitis Endoscopic Reference Score (EREFs)(secondary)	Includes additional eosinophil morphology and associated histopathologic features (e.g. degranulation, microabscesses, superficial layering, basal zone hyperplasia)
Tertiary/Exploratory		
To compare quality of life and patient reported outcomes of DED and FREE among children with eosinophilic esophagitis	PedsQL-EoE (tertiary) Pediatric Eosinophilic Esophagitis Symptom Severity Module (PEESS) (tertiary)	Determines the impact of DED and FREE on QOL and symptom severity, which is not routinely assessed.

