9.4 STATISTICAL ANALYSES

Primary analyses will assess effectiveness endpoints, including eos/hpf and EREFs. Efficacy variables will be summarized descriptively and compared between treatment groups.

Secondary analyses include descriptive statistics of the patient population (patient demographics, clinical characteristics, and comorbid conditions), concomitant medications used in this patient population and changes to these treatments.

Categorical variables will be described using frequencies and percentages while continuous variables will be described using means, standard deviations, medians, and inter-quartile ranges.

Independent sample t-tests will be conducted to compare outcomes between groups.

Additional analysis plans may be developed based on clinical considerations.

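### On the protocol's own inputs, 88% power needs an undeclared one-sided 5% test and no dropout; two-sided power is 80% at 36 per group and about 70% after the expected dropout

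*Combined protocol and SAP*

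**What the plan says.** Sections 1.1 and 9.1 both give 50% for the dairy elimination diet and 70% for the dairy plus additive diet. Section 9.1 states "a sample size of 36 enrolled patients per group (72 total) with 88% power" and adds, as a percentage, "we assume the standard deviation for both groups to be 30". Section 9.4 names the test: "Independent sample t-tests will be conducted to compare outcomes between groups".

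Other statements bear on the same calculation:

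- **Difference.** The synopsis says "we will be able to demonstrate a detectable difference of 30% among two" group comparisons, although 50% and 70% are 20 points apart.
- **Number of groups.** Section 9.1 says "we will be able to demonstrate a detectable difference between the three groups", but the trial has two arms.
- **Dropout.** The synopsis says "We estimate a 20% drop out rate among the diet elimination groups and analysis based on intention to treat".
- **Endpoint.** The synopsis defines the primary endpoint as "Histologic change differences of maximum eos/hpf baseline vs 12 week endoscopy". Section 3 adds a responder criterion: "A successful treatment outcome is < 15 eos/hpf".
- **Origin of N.** Section 9.2 says the number came from the patients thought to be available at the sites.

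No significance level, sidedness or rule for a missing week-12 biopsy appears in the document.

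**The concern.** A power figure can be checked only when the effect, its variability, the test, alpha, sidedness and the evaluable number are all fixed. Here alpha and sidedness are absent, the evaluable number is treated as equal to the enrolled number despite a stated dropout rate, and the effect is given as both 20 and 30 points.

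The scale is also unclear. An SD of 30% is possible if 50% and 70% are mean percent reductions. It is not possible if they are response rates, which is how sections 2.2 and 4.2 report dairy elimination (up to 50%). Neither reading supplies a mean difference or SD on the eos/hpf scale of the stated primary endpoint.

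This is the only power figure in the protocol, so it is the one against which a non-significant result would be weighed. With alpha and sidedness undeclared, the threshold for success could also be settled after the data are seen.

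**Working it through.** **Inputs.** Difference 20 points and SD 30 (section 9.1); independent t-test (section 9.4); 36 per group (sections 1.1 and 9.1); dropout 20% (section 1.1). Assumed: alpha 5%, and no week-12 value for dropouts, so 36 × 0.8 = 28.8, about 29 per group.

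**Formula.** Standardised difference d = 20/30 = 0.667. The noncentrality parameter is d × √(n/2), with 2n − 2 degrees of freedom. Power is the probability that a noncentral t variable exceeds the critical value.

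**Reproducing 88%.** For n = 36, noncentrality is 0.667 × √18 = 2.828.

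- One-sided 5%, critical value 1.667: power 87.6%. The normal approximation gives Φ(2.828 − 1.645) = Φ(1.183) = 88.2%. This matches the stated figure.
- Two-sided 5%, critical value 1.994: power 79.7%.

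**After dropout.** For n = 29, noncentrality is 0.667 × √14.5 = 2.539.

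| Evaluable per group | Two-sided 5% | One-sided 5% |
|---|---|---|
| 36 | 79.7% | 87.6% |
| 29 | 70.4% | 80.6% |

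**What 88% two-sided would take.** 45 evaluable per group give 87.9% and 46 give 88.6%. With 20% dropout, 46/0.8 = 57.5, or 58 enrolled per group. Alternatively, at SD 30, the difference detectable with 88% power is 0.749 × 30 = 22.5 points (n = 36) or 0.838 × 30 = 25.1 points (n = 29).

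**The 30% in the synopsis.** With SD 30, a 30-point difference at n = 36 gives 98.7% two-sided, not 88%. Read as response rates of 50% versus 80%, it gives 87.0% one-sided by exact enumeration of the chi-square test (87.8% by the unpooled normal formula) and 78.7% two-sided. That route is also one-sided, and it is not the 50% versus 70% that both sections state.

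**If 50% and 70% are response rates.** The SDs are √(0.5 × 0.5) = 50% and √(0.7 × 0.3) = 46%, not 30%. Pearson chi-square power by full binomial enumeration:

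| Case | Two-sided 5% | One-sided 5% |
|---|---|---|
| 36 per group | 41.0% | 57.1% |
| 29 per group | 33.1% | 45.8% |

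If dropouts stay in the 36 as failures, the rates become 0.5 × 0.8 = 0.40 and 0.7 × 0.8 = 0.56, and two-sided power is 26.1%.

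**On the eos/hpf scale.** Without an SD, only a standardised effect can be given. With 80% two-sided power the detectable difference is 0.67 SD at 36 per group and 0.75 SD at 29.

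**The case against.** The stated figure does reproduce, and section 9.1 words its hypothesis directionally, in favour of the additive-free arm. A one-sided test may therefore have been intended, which would make the fault one of omission rather than arithmetic. That is a fair description of how 88% may have arisen. But a directional hypothesis declares neither a one-sided test nor its alpha, and even one-sided the figure falls to 81% with 29 per group.

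Other origins are possible. For example, 45 per group gives 87.9% two-sided and 45 × 0.8 = 36, so 88% may be a pre-dropout figure attached to the wrong number. The origin is unknown, but that route would still make 88% wrong for 36 enrolled.

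The 29 per group is an assumption. The plan specifies intention-to-treat, and section 7.1 asks investigators to try to complete the final evaluation for those lost to follow-up. Some dropouts may therefore have a biopsy, and 29 is the case in which none do. Intention-to-treat defines who is analysed, however; it does not supply a missing value, and no imputation rule is given. Section 9.2 itself separates enrolled from assessable participants.

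The 80% and 70% depend on the mean-reduction reading, which the document does not confirm. That is correct; it is the more favourable of the two readings.

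Finally, feasibility set N, and this version is dated nine days before the planned end of the study on 31 July 2020. The correction can therefore change interpretation but hardly design. The mention of three groups is editorial; the version history records that an SST group was dropped.

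**Conclusion.** The concern holds. As written, 88% is not the power of a two-sided 5% test with 36 enrolled per group under any reading of 50% versus 70%. Taking difference 20, SD 30 and the t-test at face value, the two-sided chance of missing the assumed effect is 20% with everyone evaluable and 30% with 29 per group, against the 12% that 88% implies. If the percentages are response rates, it is 59% to 67%, or 74% if dropouts count as failures.

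The two-sided figure at 36 per group rests only on an assumed 5% level and the mean-reduction reading. The figures at 29 also assume that no dropout has a week-12 biopsy. Which scale the authors meant cannot be settled from the document. The point should be fixed, but it does not call for more patients.

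**What to change.** Keep N = 72 and correct sections 1.1 and 9.1:

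1. State a two-sided 5% level. If one-sided 5% was intended, declare it and report 88% falling to 81% after dropout (mean model).
2. Say whether 50%, 70% and the 30% SD are mean percent reductions in eos/hpf or whether 50% and 70% are the proportions below 15 eos/hpf. Reconcile the 20-point and 30% differences.
3. For mean reductions, replace 88% with 80% (all evaluable) to 70% (29 per group). For response rates, give 41% to 33%, add 26% for dropouts counted as failures, and delete the 30% SD.
4. For change in maximum eos/hpf, give the standardised difference detectable with 80% two-sided power: 0.67 (36 per group) to 0.75 (29 per group).
5. Label 29 per group as the case in which no dropout has a week-12 biopsy.
6. Correct the number of groups to two.
7. Say in section 9.1, as section 9.2 already does, that feasibility set the sample size.

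The cost is protocol wording and a less favourable stated power; no patients or procedures are added.

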9.2 SAMPLE SIZE DETERMINATION

The sample size was determined by pragmatic estimation of available EoE patients at each participating site. Data queries of EMRs were requested from respective IT departments to determine the number of EoE patients diagnosed in the past 12 months. Approximately 72 participants may be enrolled in the study in order to get an appropriate number of assessable participants.

9.3 POPULATIONS FOR ANALYSES

Safety analysis will be conducted on all patients evaluable for safety, defined as those patients who received any amount of study drug and provide any post-treatment safety data.

Efficacy analyses will be conducted on the intent-to-treat population, defined as all patients enrolled in the study who received patient IDs regardless of whether they received study drug or not.

9.4 STATISTICAL ANALYSES

Primary analyses will assess effectiveness endpoints, including eos/hpf and EREFs. Efficacy variables will be summarized descriptively and compared between treatment groups.

Secondary analyses include descriptive statistics of the patient population (patient demographics, clinical characteristics, and comorbid conditions), concomitant medications used in this patient population and changes to these treatments.

Categorical variables will be described using frequencies and percentages while continuous variables will be described using means, standard deviations, medians, and inter-quartile ranges.

Independent sample t-tests will be conducted to compare outcomes between groups.

Additional analysis plans may be developed based on clinical considerations.

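### The 88% power claim is not supported as written: the scale of its inputs, alpha, sidedness, the detectable difference and dropout are undefined or inconsistent

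*Combined protocol and SAP*

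**What the plan says.** The Synopsis (Section 1.1) gives the primary endpoint as "Histologic change differences of maximum eos/hpf baseline vs 12 week endoscopy". Section 3 names maximum eos/hpf as primary without the word change, and in the same row counts a value below 15 eos/hpf as treatment success.

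The power statement is in Section 9.1: "Based on histologic primary outcome efficacy estimates DED without PPI therapy (50%) compared to FREE (estimated 70" per cent), with 36 enrolled per group, 72 in total and 88% power. It continues "we assume the standard deviation for both groups to be 30" per cent, and speaks of three groups although the trial has two arms. The Synopsis repeats the 50%, 70%, 36 per group and 88%, but says "we will be able to demonstrate a detectable difference of 30% among two" groups, and then expects 20% dropout with intention-to-treat analysis.

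Section 9.2 gives another basis for the number: "The sample size was determined by pragmatic estimation of available EoE patients at each participating site". Section 9.4 plans independent-samples t-tests. No section states alpha or sidedness; the nearest hint is directional: "We hypothesize that changes in primary and secondary endpoints for FREE participants will be superior to DED".

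On labels, Section 3 lists "Eosinophilic Esophagitis Endoscopic Reference Score (EREFs)(secondary"), while Section 9.4 says "Primary analyses will assess effectiveness endpoints, including eos/hpf and EREFs".

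**The concern.** The power inputs point two ways. Sections 2.2 and 4.2 use figures of up to 50% for dairy elimination as a remission or response rate, which is a proportion. A separately assumed standard deviation of 30% and a t-test belong to a comparison of means. The plan defines no percent-change endpoint that would join the two, and it gives no difference or standard deviation in eos/hpf.

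The Synopsis then attaches the same 88% to a 30% difference, while its own two rates are 20 points apart. Dropout is mentioned beside the power figure but does not enter it, because 36 is the number enrolled.

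A reader therefore cannot tell what the 88% refers to. The choice matters: on one reading the figure stands, and on another it is less than half as large. Someone who takes 88% at face value may give a non-significant result more weight than the design can bear.

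**Working it through.** **Inputs.** 36 per arm, 50%, 70%, SD 30% (Section 9.1); 20% dropout (Section 1.1), so 36 × 0.8 = 28.8, taken as 29 per arm. Alpha 0.05 is my assumption, run one-sided (z = 1.645) and two-sided (z = 1.960).

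**Step 1: reproduce the plan's figure, reading the inputs as means.** Power = Φ(δ / [σ√(2/n)] − z), with δ = 20 and σ = 30.

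- n = 36: standard error 30 × √(2/36) = 7.071, and 20 / 7.071 = 2.828. One-sided: 2.828 − 1.645 = 1.184, power 0.882 (noncentral t: 0.876). Two-sided: 2.828 − 1.960 = 0.868, power 0.807 (t: 0.797).
- n = 29: standard error 7.878, ratio 2.539. One-sided 0.814 (t: 0.806). Two-sided 0.719 (t: 0.704).

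So 88% is reproduced one-sided, with all 36 per arm evaluable.

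**Step 2: read 50% and 70% as response rates.** Power = Φ([0.20 − z × SE0] / SE1), where SE0 = √(2 × 0.60 × 0.40 / n) and SE1 = √([0.50 × 0.50 + 0.70 × 0.30] / n).

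- n = 36: SE0 = 0.11547, SE1 = 0.11304. One-sided Φ(0.089) = 0.536; two-sided Φ(−0.233) = 0.408.
- n = 29: SE0 = 0.12865, SE1 = 0.12594. One-sided Φ(−0.092) = 0.463; two-sided Φ(−0.414) = 0.339.

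| Reading of Section 9.1 | 36 per arm, one-sided | 36, two-sided | 29 per arm, one-sided | 29, two-sided |
|---|---|---|---|---|
| Means, difference 20, SD 30 | 88% | 80–81% | 81% | 70–72% |
| Response rates 50% vs 70% | 54% | 41% | 46% | 34% |

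**Step 3: try the Synopsis's 30% at 36 per arm.** As means 30 apart with SD 30, power is 0.995 one-sided and 0.989 two-sided, well above 88%. As response rates of 50% vs 80%, it is 0.860 (pooled variance) to 0.878 (unpooled) one-sided, and 0.772 two-sided (pooled). A 30-point reading can thus also land close to 88%, so the figure alone does not show which calculation was done.

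**Step 4: the named endpoint.** Power for change in eos/hpf counts cannot be computed, since the documents give neither a difference nor an SD in those units. Free of scale, 80% power with a two-sided t-test at 0.05 needs a difference of 0.67 SD at 36 per arm, or 0.75 SD at 29.

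**The case against.** The strongest reply is that nothing is miscalculated. If 50% and 70% are mean percent reductions in eos/hpf, then the SD, the t-test and the directional hypothesis fit together and 88% follows at one-sided 0.05. Section 9.1 also ties the inputs by label to the histologic primary outcome. This stands as far as it goes: a reader might infer an arithmetic error, and the documents do not support that. But no section says that the percentages are mean reductions or that the test is one-sided, and the reading leaves the Synopsis's 30% unexplained.

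Second, Section 9.2 bases the number on available patients, so power did not set N. That also stands, and a reader who infers that N must rise goes beyond the documents. Two sections still present 88% as a property of this N, so the figure should be interpretable or be withdrawn.

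Third, efficacy is analysed by intention to treat in everyone enrolled. The plan gives no rule for a missing week-12 biopsy, so 29 per arm is a conditional figure, valid if patients without that biopsy drop out of the comparison.

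Fourth, a reader might infer from Section 9.4 that EREFs is co-primary and that multiplicity is uncontrolled. The text does not support this. Sections 1.1 and 3 fix the hierarchy, Section 9.1 separates primary from secondary endpoints, and Section 9.4 is setting effectiveness analyses against descriptive ones. Only a label needs aligning.

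**Conclusion.** The concern holds for the power statement in Section 9.1 and the Synopsis. Under an assumed alpha of 0.05, Section 9.1's inputs give 88% only as a one-sided comparison of means with no loss of biopsies. Other readings that the text allows run from 81% down to 34%, depending on scale, sidedness and evaluable numbers. The Synopsis's 30% contradicts its own rates, and the reference to three groups contradicts the design.

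It would go too far to say that the trial has less than 88% power for change in eos/hpf. On that scale power is unknown and could be higher or lower. When the results are in, the confidence interval, not the planned power, should govern how a null finding is read. The defect is in the documented justification and can be repaired without touching the design. It should be corrected; the EREFs wording is minor.

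**What to change.** With N unchanged:

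- In Section 9.1 and the Synopsis, state whether 50%, 70% and SD 30% are response rates or mean percent reductions, and give alpha and sidedness. If they are response rates, remove the separate SD.
- Correct the 30% difference to 20 points, or change the rates so that they differ by 30. Change three groups to two.
- Replace 88% with the power that follows from those choices at the number expected to have a week-12 biopsy, and state how missing biopsies are handled. The table above gives the values for 36 and 29 per arm.
- Say that 72 rests on feasibility, as Section 9.2 does. Say that power for change in eos/hpf counts was not calculated, unless an SD labelled as an assumption is supplied.
- Report the plan's own success criterion (below 15 eos/hpf at week 12) as a secondary proportion with a risk difference and 95% CI. At 50% vs 70% the half-width is 1.96 × 0.11304, about 22 points, at 36 per arm and about 25 points at 29.
- In Section 9.4, name change in maximum eos/hpf as the single primary analysis and EREFs as secondary. Add the word change in Section 3 to match the Synopsis.

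The cost is wording in Sections 1.1, 3, 9.1 and 9.4 and one summary from biopsies already planned. The downside is that the stated power becomes less favourable on most readings. It stays near 88% for the 20-point difference only if a one-sided 0.05 test of means with no loss of biopsies is declared.
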